9.2.3 Safety Analysis Plan

All safety analyses will be based on the SAF population.

The analysis of safety will be based on the occurrence of AEs, the results of the safety laboratory tests, and the occurrence of parvovirus B19 seroconversions.

AEs will be coded according to the latest Medical Dictionary for Regulatory Activities (MedDRA) version. The analysis will include only treatment-emergent adverse events (TEAEs), i.e., AEs that started or worsened after the first IMP infusion. All TEAEs, related TEAEs (i.e., TEAEs probably or possibly related to the IMP), and serious TEAEs will be summarised and tabulated according to MedDRA primary system organ class and preferred term.

Patient listings will be provided for patients with SAEs, AEs leading to withdrawal from study, and AEs leading to death.

Time profiles of the safety laboratory parameters will be analysed by presenting sampling statistics for the values as well as their difference to baseline at each time point. Additionally, frequency tables for values outside the normal ranges will be presented.

Similarly, time profiles of VWF and FVIII inhibitor testing results will be analysed by presenting sampling statistics for the values as well as frequency tables for positive findings, along with 95% Pearson-Clopper CIs.

To assess the viral safety of *Wilate*, incidences of parvovirus B19 seroconversions between baseline and end of study will be estimated along with 95% Pearson-Clopper CIs.

Other safety parameters (e.g., changes in physical examination findings) will be analysed by summary tables or listings.

The analysis of the safety parameters recorded during surgery (lab values) will be purely descriptive and presented as summary tables or listings.

9.2.4 Handling of Missing Data

In general, missing data will not be imputed. Calculations pertaining to the derivation of the TABR will be based on documented time periods only.

Only in case of missing body weight will the last available weight measurement be used for calculating the dose per kg bodyweight (last observation carried forward, LOCF).

9.3 Randomisation, Stratification, and Code Release

Not applicable.

9.4 Interim Analysis

Not applicable.

10 ETHICAL/REGULATORY, LEGAL AND ADMINISTRATIVE ASPECTS

10.1 Ethical/Regulatory Framework

This study will be conducted in accordance with the ethical principles laid down in the Declaration of Helsinki. The study protocol and any subsequent amendment(s) will be submitted to an Independent Ethics Committee (IEC)/Institutional Review Board (IRB) and to the Regulatory Authority. The study will be conducted in compliance with the protocol, GCP guidelines, and applicable regulatory requirements.

The regulatory application or submission for regulatory approval will be made by the Sponsor or designated third party (e.g., CRO) as required by national law.

10.2 Approval of Study Documents

The study protocol, a sample of the patient information and informed consent form, any other materials provided to the patients, and further requested information will be submitted by the Sponsor or the investigator to the appropriate IEC/IRB and the Regulatory Authority. The study must be approved by the IEC/IRB and the Regulatory Authority before any IMP may be shipped to the study sites and any patient is exposed to a study-related procedure.

The Sponsor, the investigator, and any third party (e.g., CRO) involved in obtaining approval must inform each other in writing that all ethical and legal requirements have been met before the first patient is enrolled in the study.

10.3 Patient Information and Informed Consent

The investigator will obtain freely given written consent from each patient after an appropriate explanation of the aims, methods, anticipated benefits, potential hazards, and any other aspect of the study which is relevant to the patient's decision to participate. The informed consent form must be signed, with name and date and time noted by the patient, before the patient is exposed to any study-related procedure, including screening tests for eligibility.

For patients not qualified to give legal consent, written consent must be obtained from the legal parent/guardian. If children are old enough to understand the risks and benefits of the study, they should also be informed and provide their oral or written assent.

The investigator will explain that the patients are completely free to refuse to enter the study or to withdraw from it at any time, without any consequences for their further care and without the need to justify. The investigator will complete the informed consent section of the eCRF for each patient enrolled.

Each patient will be informed that his medical (source) records may be reviewed by the study monitor, a quality assurance auditor, or a health authority inspector, in accordance with applicable regulations, and that these persons are bound by confidentiality obligations.

10.4 Protocol Amendments

Any prospective change to the protocol will be agreed between the Co-ordinating Investigator and the Sponsor prior to its implementation. Any such amendments will be submitted to the IEC/IRB and/or competent authority responsible as required by applicable regulations.

IEC/IRB approval will, at a minimum, be requested for any change to this protocol which could affect the safety of the patients, the objective/design of the study, any increase in dosage or duration of exposure to the IMP, an increase in the number of patients treated, the addition of a new test or procedure, or the dropping of a test intended to monitor safety.

10.5 Confidentiality of Patient Data

The investigator will ensure that the patient's confidentiality is preserved. On CRFs or any other documents submitted to the Sponsor, the patients will not be identified by their names, but by a unique patient identifier. Documents not intended for submission to the Sponsor, i.e., the confidential patient identification code list, original consent and assent forms, and source records, will be maintained by the investigator in strict confidence.

11 QUALITY CONTROL AND QUALITY ASSURANCE

11.1 Periodic Monitoring

The monitor will contact and visit the investigator periodically to review all study-related source data/records, verify the adherence to the protocol and the completeness, correctness and accuracy of all eCRF entries compared to source data. The investigator will co-operate with the monitor to ensure that any discrepancies identified are resolved.

For this study, the first monitoring visit shall take place shortly after the inclusion of the first patient. Thereafter, monitoring frequency will depend on study progress.

The monitor must be given direct access to source documents (original documents, data and records). Direct access includes permission to examine, analyse, verify, and reproduce any records and reports that are important to the evaluation of the clinical study. Source data will be available for all data in the eCRFs, including all laboratory results.

11.2 Audit and Inspection

The investigator will make all study-related source data and records available to a qualified quality assurance auditor mandated by the Sponsor, or to IEC/IRB/regulatory inspectors, after reasonable notice. The main purposes of an audit or inspection are to confirm that the rights and welfare of the patients have been adequately protected, and that all data relevant for the assessment of safety and efficacy of the IMP have been reported to the Sponsor.

12 REPORTING AND PUBLICATION

12.1 Clinical Study Report

A clinical study report (in accordance with relevant guidelines and the Sponsor's Standard Operating Procedures) will be prepared by the Sponsor after completion of the study. The Co-ordinating Investigator will approve the final study report after review.

12.2 Publication Policy

The results of this study may be published or presented at scientific meetings.

If this is envisaged by an investigator, the investigator agrees to inform the Sponsor and to submit all manuscripts or abstracts to the Sponsor prior to submission to an editorial board or scientific review committee. This will allow the Sponsor to protect proprietary information and to provide comments based on information that may not yet be available to the investigator.

In accordance with standard editorial and ethical practice, the Sponsor will support publication of multi-centre studies only in their entirety and not as individual centre data. Authorship will be determined by mutual agreement.

13 LIABILITIES AND INSURANCE

In order to cover any potential damage or injury occurring to a patient in association with the IMP or participation in the study, the Sponsor will contract insurance in accordance with local regulations.

The investigator is responsible for dispensing the IMP according to this protocol and for its secure storage and safe handling throughout the study.

Property of Octapharma. Do not copy or distribute without written permission.

15 APPENDICES

Not applicable.

Property of Octapharma. Do not copy or distribute without written permission.

Statistical Analysis Plan	Version 6.0		Page 1 of 24
Sponsor	Octapharma	Protocol No	WIL-31

Statistical Analysis Plan (SAP)

Sponsor:	Octapharma
Study Title:	Clinical Study to Investigate the Efficacy and Safety of Wilate during Prophylaxis in Previously Treated Patients with VWD
Protocol Version/Date:	Ver. 07, 2021-03-01; Ver. 08, 2021-03-01 (Ukraine only)
SAP Version/Date:	Ver. 6.0, 2022-09-23
Supersedes SAP Version:	Ver. 5.0, 2022-05-18
Appendices (external documents):	1. List of Tables, Listing, Figures (TLFs)

Approval

The Trial Statistician hereby confirms that the SAP was prepared in conformance with the procedures and principles set forth in the indicated protocol version and all established relevant guidelines.

Name Affiliation, Function	Signature:	Date:
██ Ergomed, Trial Statistician		

By signing hereafter, I confirm that this Statistical Analysis Plan adequately describes the statistical analyses to be performed in the context of this study.

Name Affiliation, Function	Signature:	Date:
██ Octapharma		
██ Octapharma		

Statistical Analysis Plan	Version 6.0		Page 2 of 24
Sponsor	Octapharma	Protocol No	WIL-31

Revision history

SAP Version	Version date	Reason(s) for change
1.0	2018-12-18	Initial version
1.1	2019-02-08	Trial Flow Charts were adapted.
2.0	2019-06-21	
- adding age and race subgroup analyses- adding non-parametric test for primary endpoint TABR- adapting to new IVR visit schedule- addressing handling of menstrual bleeds- adding comparisons with historical data obtained during on-demand treatment periods
3.0	2020-03-26	
- changing to new SAP template,- addressing changes in protocol versions 05 and 06 respectively protocol amendment #3 and #1-UKA
4.0	2022-05-10	
- Modifications and addition of definitions/formulas for derived variables in section 6.1.- Definition for modified FAS and PK PP set added.- For comparison of annualized bleeding rates, instead of a paired t-test for the log-transformed data a negative binomial counting regression model (GLIM) will be used (section 2.2)- Usage of on-demand run-in trial data defined in detail and adapted to the fact that all subjects participated in previous WIL-29 study (usage of retrospective measurements is not applicable)- Further changes after cross-check with protocol and as requested by sponsor as well as minor changes in wording

Abbreviation	Description
ABR _{od}	Annualized bleeding rate under on-demand treatment (WIL-29 run-in study)
ABRpr	Annualized bleeding rate under prophylactic treatment (study WIL-31)
ADR	Adverse drug reaction
AE	Adverse Event
ALAT	ALanine Amino Transferase
ASAT	ASpartate Transaminase
BE	Bleeding Episode
BMI	Body Mass Index
BW	Body Weight
CHR	Chromogenic assay
CI	Confidence Interval
CL	Clearance
C ₀	Last concentration before IMP administration
C _{max}	Maximum Plasma Concentration
CRF	Case Report Form
CRO	Contract Research Organization
CSR	Clinical Study Report
DMP	Data Management Plan
DRM	Database Review Meeting
DVP	Data Validation Plan
ED	Exposure Day
eCRF	Electronic Case Report Form
FAS	Full Analysis Set
FVIII	Coagulation Factor VIII
FVIII:C	Factor VIII-coagulant
HJHS	Hemophilia Joint Health Score
HMABR	Heavy Menstrual Annualized Bleeding Rate
ID	Identifier
IMP	Investigational Medicinal Product
ITT	Intention-To-Treat
IU	International Unit
IV	Intravenous
IVR	Incremental in Vivo Recovery
LOCF	Last Observation Carried Forward
mFAS	modified Full Analysis Set
PK-PP	Pharmacokinetic Per-Protocol set
MedDRA	Medical Dictionary for Regulatory Activities
MRT	Mean Residence Time
N	Number of Subjects/Observations
OS	One-stage assay
POP	Postoperative
PBAC	Pictorial Blood Assessment Chart
PK	Pharmacokinetic, Pharmacokinetic set
PP	Per-Protocol
PT	Preferred Term

Statistical Analysis Plan	Version 6.0		Page 5 of 24
Sponsor	Octapharma	Protocol No	WIL-31

Abbreviation	Description
PROMIS-29	Patient-Reported Outcomes Measurement Information System
PT	Preferred Term
QC	Quality Control
RBC	Red Blood Cell count
SAE	Serious Adverse Event
SAF	Safety Analysis Set
SAP	Statistical Analysis Plan
SAS	Statistical Analysis Software package
SD	Standard Deviation
SP	Statistical Programmer
SOC	System Organ Class
SOP	Standard Operating Procedure
SABR	Spontaneous Annualized Bleeding Rate
SURG	Surgery analysis set
TABR	Total Annualized Bleeding Rate
TRABR	Traumatic Annualized Bleeding Rate
TEAE	Treatment Emergent Adverse Event
TLFs	Tables, Listings, Figures
TS	Trial Statistician
VWD	Von Willebrand Disease
VWF	Von Willebrand Factor
VWF:Ac	VWF activity
VWF:GP1bM	Assay based on the spontaneous binding of VWF to a gain-of-function mutant GP1b fragment
VWF:RCO	Ristocetin cofactor activity; assay that uses platelets and ristocetin
WBC	White Blood Cell count
WHO	World Health Organization

Property of Octapharma. Don't copy or distribute without written permission.

Statistical Analysis Plan	Version 6.0		Page 6 of 24
Sponsor	Octapharma	Protocol No	WIL-31

1 STUDY INFORMATION

1.1 Primary objective

The primary objective of this study is to determine the efficacy of *Wilate* in the prophylactic treatment of previously treated patients with type 3, type 2 except N, and severe type 1 VWD.

1.2 Secondary objective

The secondary objectives of this study are:

- Assess the incremental IVR of VWF:Ac and FVIII:C over time (at baseline, and at 1, 2, 3, 6, 9 and 12 months of treatment)
- Determine the pharmacokinetics (PK) of *Wilate* for VWF:Ac and FVIII:C in paediatric patients aged 6–16 years
- Assess the safety and tolerability of *Wilate* during prophylaxis
- Determine *Wilate* consumption data

1.3 Additional objective

Additional objectives of this study are to:

- Determine the efficacy of *Wilate* in the treatment of breakthrough bleeding episodes (BEs)
- Determine the efficacy of *Wilate* in surgical prophylaxis
- Assess patients' Quality of Life (QoL) during prophylaxis with *Wilate*
- Assess patients' joint status using the Hemophilia Joint Health Score (HJHS)
- Assess the menstrual bleeding intensity of female patients of child-bearing potential (based on PBAC score)

1.4 Study design

This study is designed as a prospective, non-controlled, international, multi-center phase 3 study.

It is intended to compare the prospectively obtained assessments under a prophylactic treatment regimen with similar assessment under an on-demand treatment regimen. To achieve this, retrospective data from the patient's medical records or patient data obtained in a similar (prospective) study with an on-demand treatment regimen will be used for the analysis.

Further details are given in the overview on next page.

1.5 Planned sample size

Overall, 28 patients will be enrolled in this study, including at least 5 patients with VWD type 3, at least 5 patients aged 6–11 years, and at least 5 patients aged 12–16.

Assuming a mean total annualized bleeding rate (TABR) ratio (TABR_{pr} / TABR_{od}) of 0.25 with a correlation of 0.5 between the two treatment regimes, a coefficient of variation of 10 in on-demand treatment, and a coefficient of variation of 10 in prophylactic treatment, 25 patients will be needed to reject the null hypothesis

Statistical Analysis Plan	Version 6.0		Page 7 of 24
Sponsor	Octapharma	Protocol No	WIL-31

$$H_0: \text{mean}(\text{TABR}_{\text{pr}} / \text{TABR}_{\text{od}}) \geq 0.5$$

in favor of

$$H_1: \text{mean}(\text{TABR}_{\text{pr}} / \text{TABR}_{\text{od}}) < 0.5$$

with a type one error of 0.025 and power of 80% using a paired t-test for log-transformed data.

TABR_{pr} is defined as the total annual bleeding rate in the prophylactic treatment and TABR_{od} is defined as the total annual bleeding rate in the matching on-demand treatment period.

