2.2 Deviations from the trial protocol with regard to statistical analyses

Due to the reporting of non-confirmed eligibility, the primary and secondary efficacy analyses will also be performed for the mFAS (see section 3.3).

Contrary to initial assumptions, patients may have documented 0 bleeding episodes during the prophylactic treatment phase. This would contradict the assumption of a log-normally distributed TABR and make the calculation of logarithms of the TABRs impossible. Hence, instead of the originally planned paired t-test for the log-transformed data, now the use of a negative binomial counting regression model (GLIM) with treatment regimen as main effect and treatment period as offset parameter is implemented for the analysis of the primary efficacy parameter.

Such counting regression models will also be used for the analysis of similarly defined secondary and exploratory endpoints (e.g. SABR).

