4.1.4 Use of measurements from on-demand non-interventional run-in study (WIL-29)

Apart from analyzing the efficacy of Wilate in the prophylactic treatment of VWD based on annualized bleeding rates, it is also of interest to compare data with annualized bleeding rated of the same patients under an on-demand treatment schedule. To achieve this, data from those patients that also participated in a previous on-demand run-in study (WIL-29) will be used in the analysis data for the current study. This includes duration of On-demand phase, number of bleeding episodes and annualized bleeding rates for total, spontaneous, traumatic, and heavy menstrual bleeds.

For females with childbearing potential, it is of interest to compare their differences in median PBAC scores under prophylaxis with scores under on-demand treatment. For this purpose, all total PBAC scores collected during study WIL-29 will be stored in the WIL-31 database and the Wilcoxon matched pair sign-rank test will be used for statistical comparison.

The statistical methods for such exploratory comparisons of on-demand to prophylactic treatment schedule will be based on paired, or repeated-measurement data.

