4.7.1 Primary Endpoint

Primary objective of this study is to demonstrate that the total annualized bleeding rate (TABR) during prophylactic treatment lowers the patients' TABR during on-demand treatment by more than 50%.

TABR will be calculated as the total number of spontaneous, traumatic and other bleeds (excluding menstrual bleeds) in the time period between first prophylactic dose of IMP and the day of the last dose of IMP (+ 2 days wash-out), divided by the duration (in years) between first dose of prophylactic IMP and the day of last dose of IMP (+ 2 days wash-out). Surgery periods, and BEs occurring within these periods, will be excluded from the calculation of TABR. Menstrual bleeds of any severity will not be included in this calculation. In female patients with child-bearing potential heavy menstrual bleeds will be reported and analyzed separately.

For this efficacy assessment the individual annualized bleeding rates under prophylactic treatment in this study will be compared to the annualized bleeding rates recorded for the same patient during a previous, non-interventional study, (WIL-29).

To test whether the mean TABR during prophylactic treatment ($TABR_{pr}$) is less than half the historical mean TABR during on-demand treatment ($TABR_{od}$), the following pair of hypotheses will be tested in the context of negative binomial counting regression model:

$$(*) H_0: \text{mean}(TABR_{pr} / TABR_{od}) \geq 0.5 \quad \text{vs} \quad H_1: \text{mean}(TABR_{pr} / TABR_{od}) < 0.5$$

at a one-sided alpha level of 2.5%. A corresponding two-sided 95% CI for the different TABRs and their ratio will also be provided.

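### SAP 1.5 still quotes 80% power for the replaced paired t-test, the primary negative binomial model has no defined within-patient term, and 28/5/5 enrolment is not reconciled with the protocol's 40/6/6

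*SAP*

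**What the plan says.** **Sample size.** SAP 1.5 assumes a bleeding-rate ratio of 0.25 against a null of 0.5, a correlation of 0.5 and a coefficient of variation of 10 in each period. It concludes that 25 patients suffice "with a type one error of 0.025 and power of 80% using a paired t-test for log-transformed data". Protocol 9.1 makes the same calculation.

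**Primary test.** SAP 2.2 explains that patients may have no bleeds on prophylaxis, so logarithms may not exist. The t-test gives way to a "negative binomial counting regression model (GLIM) with treatment regimen as main effect and treatment period as offset parameter". SAP 4.7.1 agrees: "the following pair of hypotheses will be tested in the context of negative binomial counting regression model".

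**Pairing.** SAP 4.7.1 says that each patient's rates on prophylaxis "will be compared to the annualized bleeding rates recorded for the same patient during a previous, non-interventional study, (WIL-29"). SAP 4.1.4, on using the WIL-29 data, says that the methods for "such exploratory comparisons of on-demand to prophylactic treatment schedule will be based on paired, or repeated-measurement data". Neither section names a random effect, a GEE or any other patient-level term.

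**Enrolment.** SAP 1.5 says "Overall, 28 patients will be enrolled in this study", with "at least 5 patients aged 6–11 years, and at least 5 patients aged 12–16". The SAP title page cites protocol versions "Ver. 07, 2021-03-01; Ver. 08, 2021-03-01 (Ukraine only"). Protocol version 07 (synopsis, 3.2 and 4.1.1) plans around 40 patients with at least 6 in each of those age groups, and 3.2 wants at least 25 evaluable for the primary endpoint.

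**The concern.** A reader of SAP 1.5 would take 80% as the power of the primary analysis. It belongs to a test that will not be run, and the section neither says so nor points to 2.2.

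The more consequential gap is the model. Each patient supplies two records, one on demand and one on prophylaxis. A regression with only regimen and offset treats them as independent. A programmer could fit that model, a random-intercept model or a GEE and claim to follow the SAP each time. The three give different standard errors, so the confidence interval and p-value of the primary result are not fixed in advance.

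The enrolment mismatch is a separate documentary fault: the SAP states a different trial size from the protocol version it cites.

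**Working it through.** **1. Reproduce the plan's figure.** Inputs (SAP 1.5 and 4.7.1): ratio 0.25, null 0.5, correlation 0.5, CV 10, one-sided 2.5%. Take CV 10 as 1000% and the correlation on the raw scale.

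- Variance of the log ratio = 2[ln(1 + CV²) − ln(1 + ρCV²)] = 2(ln 101 − ln 51) = 1.3666, so SD = 1.169.
- Effect = ln(0.5/0.25) = 0.693.
- Noncentrality at n=25 = 0.693 × 5 / 1.169 = 2.96.
- Noncentral t power: 81.2% at n=25 and 79.4% at n=24.

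So 25 is the smallest n that reaches 80%. With the correlation on the log scale, the variance is 2 × (1 − 0.5) × ln 101 = 4.615, power at 25 is 34% and 78 patients would be needed. With CV read as 10%, n is 3. Only the first reading gives the plan's figure.

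**2. What omitting the patient term does.** For log rates, the variance of the period difference is V(pr) + V(od) − 2Cov. A model with independent records drops 2Cov. With positive correlation the standard error is then too large.

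**3. Illustrative power and size of the model as written in SAP 2.2.** The documents give no on-demand rate, so everything here is assumed:

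- patient rates are bivariate log-normal with raw-scale correlation 0.5 and Poisson counts;
- 0.5 year on demand and 1 year on prophylaxis, n=25;
- Wald test against ln 0.5, true ratio 0.25 for power and 0.5 for size.

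| CV | On-demand rate/yr | Power |
|---|---|---|
| 1 | 12 | about 75–76% |
| 1 | 48 | about 87% |
| 10 | 12 | about 17–18% |
| 10 | 48 | about 25% |

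Size at CV 1 is about 0.9–1.5% against a nominal 2.5%. At CV 10 a check put it close to nominal, so the conservative size is a result for CV 1 and not a general one.

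**4. A different data model.** With gamma patient and period effects at n=25, two null scenarios gave a size of 0.6–1.3% for the unpaired fit and about 5–6% with uncorrected patient-clustered standard errors. In one middle scenario (25 bleeds per year, both variances 0.5) power was about 68% unpaired and 80% clustered, but the two tests do not have the same size. The way pairing enters therefore moves both size and power.

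**5. Enrolment side by side.**

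| | SAP 1.5 | Protocol version 07 |
|---|---|---|
| Total | 28 | around 40 |
| Aged 6–11 | at least 5 | at least 6 |
| Aged 12–16 | at least 5 | at least 6 |
| Type 3 | at least 5 | at least 5 |

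SAP 2.2 lists the mFAS and the model change only. No revision-history entry mentions enrolment.

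**The case against.** The test switch is openly disclosed: SAP 2.2 gives the reason and the version 4.0 revision entry logs it. SAP 1.5 describes planned sample size and matches protocol 9.1, and keeping a planning calculation is normal practice. SAP version 6.0 is dated 2022-09-23, after the planned clinical end of Q1 2022, so a new power figure would change no decision. All this stands. It is why the remedy for 1.5 is a label, with a new simulation optional.

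On pairing, a reader might infer that the SAP is silent. It is not. SAP 4.1.4 covers the WIL-29 total bleeding rates and states a paired or repeated-measurement basis, and 4.7.1 compares each patient with himself or herself. What is missing is the model term, and the exploratory label leaves it open whether 4.1.4 governs the primary test at all.

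SAP 2.2 concerns statistical analyses, so enrolment counts need not be listed there. That is fair, but no other section or revision entry records them either.

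A reader might also infer that 28 leaves only 28 − 25 = 3 patients to spare for drop-out. The documents do not support this. Patients dosed after the baseline visit stay in the FAS (SAP 3.2), the mFAS removes only those whose VWD type is unconfirmed (SAP 3.3), and rates use documented time (SAP 4.1.2). Someone who leaves early still counts, with shorter exposure. The protocol does not define evaluable, and 28 exceeds 25.

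**Conclusion.** The point holds as a mismatch between sections, with high confidence on the text and moderate confidence on the simulated sizes. The 80% is correct for the paired log t-test and does not carry over to the negative binomial model. The primary model's within-patient structure is undefined, and the version in 2.2, fitted literally, has the wrong standard error. The SAP's 28/5/5 conflicts with the protocol's 40/6/6 without explanation.

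A reader might infer from the 17–25% at CV 10 that the trial is underpowered. The documents do not show that. The figure rests on assumed rates and an extreme spread, and at CV 1 the same model has about 75–87%. Nor may one restrict the simulated patients to those with at least six on-demand bleeds and conclude that power is ample. That selects on the count being analysed, which builds in regression to the mean, and the second entry route in protocol 4.1.2 sets no such minimum.

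**What to change.** 1. In SAP 2.2 and 4.7.1, name the within-patient term of the primary negative binomial model. Examples are a patient random intercept, or a GEE with a small-sample correction, since uncorrected clustered errors are too liberal at n=25. In 4.1.4, make clear that the TABR comparison is the primary analysis and not exploratory.
2. In SAP 1.5, label the 80% as the planning figure for the superseded t-test, refer to 2.2, and do not quote it for the new model. A simulated power for the chosen model is optional; if given, it should state the assumed CV, on-demand rate and correlation.
3. Reconcile 28/5/5 with 40/6/6, or record the change and its reason.

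No extra patients are needed. The cost is some SAP wording, and any power that is stated may look less favourable than 80%.
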